5.3 Preparation and Administration of Study Drugs

A research supply of Pembrolizumab will be supplied by Merck. It will be shipped to, stored and dispensed from Investigational Drug Services (IDS) of the Hospital of the University of Pennsylvania and Penn Presbyterian Medical Center for patients enrolled at that site. The drug preparation will be done in the pharmacy.

The investigator shall take responsibility for and shall take all steps to maintain appropriate records and ensure appropriate supply, storage, handling, distribution and usage of investigational product in accordance with the protocol and any applicable laws and regulations.

Clinical Supplies will be provided by Merck as summarized in Table 2.

Table 2: Product Descriptions

Product Name and Potency	Dosage Form
Pembrolizumab 100 mg/4mL	Solution for injection

Study Medication Administration

Pembrolizumab will be administered as a 30 minute intravenous infusion (treatment cycle intervals may be increased due to toxicity as described in Table 1). Sites should make every effort to target infusion timing to be as close to 30 minutes as possible. However, given the variability of infusion pumps from site to site, a window of -5 minutes and +10 minutes is permitted (i.e., infusion time is 30 minutes: -5 min/+10 min).

Phase II Pembrolizumab Reirradiation

Pembrolizumab Premedication

Patients do not require premedication prior to Pembrolizumab administration, as hypersensitivity reactions are rare.

5.4 Subject Compliance Monitoring

The study team will track subject compliance with the treatment regimen at each visit and note the dose, date, and time of study medication administration on the case report form. If there are any significant irregularities in compliance (in the opinion of the investigator), the subject should be withdrawn from the study. Interruptions from the protocol specified treatment plan for greater than 12 weeks between Pembrolizumab doses due to toxicity will require consultation between the investigator and the medical monitor and written documentation of the collaborative decision on subject management.

5.5 Prior and Concomitant Therapy

Medications or vaccinations specifically prohibited in the exclusion criteria are not allowed during the ongoing trial. If there is a clinical indication for one of these or other medications or vaccinations specifically prohibited during the trial, discontinuation from trial therapy or vaccination may be required. The investigator should discuss any questions regarding this with the Sponsor. The final decision on any supportive therapy or vaccination rests with the investigator and/or the subject's primary physician. However, the decision to continue the subject on trial therapy or vaccination schedule requires the mutual agreement of the Investigator, the Sponsor, and the subject.

5.5.1 Acceptable Concomitant Medications

All treatments that the investigator considers necessary for a subject's welfare may be administered at the discretion of the investigator in keeping with the community standards of medical care. All concomitant medications will be recorded in the subject's medical record including all prescription, over-the-counter (OTC), herbal supplements, and IV medications and fluids. If changes occur during the trial period, documentation of drug dosage, frequency, route, and date may also be included in the medical record. Examples of acceptable concomitant medications include zoledronic acid, denosumab, megestrol acetate, and cannabinoids.

All concomitant medications received within 28 days before the first dose of trial treatment and 30 days after the last dose of trial treatment should be recorded. Concomitant medications administered after 30 days after the last dose of trial treatment should be recorded for SAEs and ECIs.

5.5.2 Prohibited Concomitant Medications

Subjects are prohibited from receiving the following therapies during the Pre-Pembrolizumab Screening and Pembrolizumab Treatment Phase of this trial:

- Anti-cancer systemic chemotherapy or biological therapy
- Immunotherapy not specified in this protocol
- Investigational agents other than Pembrolizumab
- Radiation therapy
 - Note: Radiation therapy to a symptomatic solitary lesion or to the brain may be allowed after consultation with Sponsor, but would be regarded as a disease progression event for the primary outcome.
- Live vaccines within 30 days prior to the first dose of trial treatment and while participating in the trial. Examples of live vaccines include, but are not limited to, the following: measles, mumps, rubella, chicken pox, yellow fever, rabies, BCG, and typhoid (oral) vaccine. Seasonal

Phase II Pembrolizumab Reirradiation

influenza vaccines for injection are generally killed virus vaccines and are allowed; however intranasal influenza vaccines (e.g. Flu-Mist®) are live attenuated vaccines and are not allowed.

- Glucocorticoids for any purpose other than an abbreviated course to modulate symptoms from an event of clinical interest of suspected immunologic etiology. The use of physiologic replacement doses of corticosteroids may be approved after consultation with the Sponsor.

Subjects who, in the assessment by the investigator, require the use of any of the aforementioned treatments for clinical management should be removed from the trial. Subjects may receive other medications that the investigator deems to be medically necessary.

There are no prohibited therapies during the Post-Treatment Follow-up Phase.

5.6 *Rescue Medications and Supportive Care*

5.6.1 *Supportive Care Guidelines*

Subjects should receive appropriate supportive care measures as deemed necessary by the treating investigator. Suggested supportive care measures for the management of adverse events with potential immunologic etiology are outlined below. Where appropriate, these guidelines include the use of oral or intravenous treatment with corticosteroids as well as additional anti-inflammatory agents if symptoms do not improve with administration of corticosteroids. Note that several courses of steroid tapering may be necessary as symptoms may worsen when the steroid dose is decreased. For each disorder, attempts should be made to rule out other causes such as metastatic disease or bacterial or viral infection, which might require additional supportive care. The treatment guidelines are intended to be applied when the investigator determines the events to be related to pembrolizumab.

Note: if after the evaluation the event is determined not to be related, the investigator does not need to follow the treatment guidance (as outlined below). Refer to Section 5.2.1 for dose modification.

It may be necessary to perform conditional procedures such as bronchoscopy, endoscopy, or skin photography as part of evaluation of the event.

- **Pneumonitis:**
 - For **Grade 2 events**, treat with systemic corticosteroids. When symptoms improve to Grade 1 or less, steroid taper should be started and continued over no less than 4 weeks.
 - For **Grade 3-4 events**, immediately treat with intravenous steroids. Administer additional anti-inflammatory measures, as needed.
 - Add prophylactic antibiotics for opportunistic infections in the case of prolonged steroid administration.
- **Diarrhea/Colitis:**

Subjects should be carefully monitored for signs and symptoms of enterocolitis (such as diarrhea, abdominal pain, blood or mucus in stool, with or without fever) and of bowel perforation (such as peritoneal signs and ileus).

 - All subjects who experience diarrhea/colitis should be advised to drink liberal quantities of clear fluids. If sufficient oral fluid intake is not feasible, fluid and electrolytes should be substituted via IV infusion. For Grade 2 or higher diarrhea, consider GI consultation and endoscopy to confirm or rule out colitis.
 - For **Grade 2 diarrhea/colitis**, administer oral corticosteroids.
 - For **Grade 3 or 4 diarrhea/colitis**, treat with intravenous steroids followed by high dose oral steroids.
 - When symptoms improve to Grade 1 or less, steroid taper should be started and continued over no less than 4 weeks.

Phase II Pembrolizumab Reirradiation

- **Type 1 diabetes mellitus (if new onset, including diabetic ketoacidosis [DKA]) or ≥ Grade 3 Hyperglycemia, if associated with ketosis (ketonuria) or metabolic acidosis (DKA)**
 - For **T1DM** or **Grade 3-4** Hyperglycemia
 - Insulin replacement therapy is recommended for Type 1 diabetes mellitus and for Grade 3-4 hyperglycemia associated with metabolic acidosis or ketonuria.
 - Evaluate patients with serum glucose and a metabolic panel, urine ketones, glycosylated hemoglobin, and C-peptide.
- **Hypophysitis:**
 - For **Grade 2** events, treat with corticosteroids. When symptoms improve to Grade 1 or less, steroid taper should be started and continued over no less than 4 weeks. Replacement of appropriate hormones may be required as the steroid dose is tapered.
 - For **Grade 3-4** events, treat with an initial dose of IV corticosteroids followed by oral corticosteroids. When symptoms improve to Grade 1 or less, steroid taper should be started and continued over no less than 4 weeks. Replacement of appropriate hormones may be required as the steroid dose is tapered.
- **Hyperthyroidism or Hypothyroidism:**

Thyroid disorders can occur at any time during treatment. Monitor patients for changes in thyroid function (at the start of treatment, periodically during treatment, and as indicated based on clinical evaluation) and for clinical signs and symptoms of thyroid disorders.

 - **Grade 2** hyperthyroidism events (and **Grade 2-4** hypothyroidism):
 - In hyperthyroidism, non-selective beta-blockers (e.g. propranolol) are suggested as initial therapy.
 - In hypothyroidism, thyroid hormone replacement therapy, with levothyroxine or liothyroinine, is indicated per standard of care.
 - **Grade 3-4** hyperthyroidism
 - Treat with an initial dose of IV corticosteroid followed by oral corticosteroids. When symptoms improve to Grade 1 or less, steroid taper should be started and continued over no less than 4 weeks. Replacement of appropriate hormones may be required as the steroid dose is tapered.
- **Hepatic:**
 - For **Grade 2** events, monitor liver function tests more frequently until returned to baseline values (consider weekly).
 - Treat with IV or oral corticosteroids
 - For **Grade 3-4** events, treat with intravenous corticosteroids for 24 to 48 hours.
 - When symptoms improve to Grade 1 or less, a steroid taper should be started and continued over no less than 4 weeks.
- **Renal Failure or Nephritis:**
 - For **Grade 2** events, treat with corticosteroids.
 - For **Grade 3-4** events, treat with systemic corticosteroids.
 - When symptoms improve to Grade 1 or less, steroid taper should be started and continued over no less than 4 weeks.
- **Management of Infusion Reactions:** Signs and symptoms usually develop during or shortly after drug infusion and generally resolve completely within 24 hours of completion of infusion.

Phase II Pembrolizumab Reirradiation

The table below shows treatment guidelines for subjects who experience an infusion reaction associated with administration of pembrolizumab (MK-3475).

Table 1 Infusion Reaction Treatment Guidelines

NCI CTCAE Grade	Treatment	Premedication at subsequent dosing
Grade 1 Mild reaction; infusion interruption not indicated; intervention not indicated	Increase monitoring of vital signs as medically indicated until the subject is deemed medically stable in the opinion of the investigator.	None
Grade 2 Requires infusion interruption but responds promptly to symptomatic treatment (e.g., antihistamines, NSAIDS, narcotics, IV fluids); prophylactic medications indicated for < =24 hrs	
Stop Infusion and monitor symptoms. Additional appropriate medical therapy may include but is not limited to:
 
 IV fluids Antihistamines NSAIDS Acetaminophen Narcotics 
Increase monitoring of vital signs as medically indicated until the subject is deemed medically stable in the opinion of the investigator.
 
If symptoms resolve within one hour of stopping drug infusion, the infusion may be restarted at 50% of the original infusion rate (e.g., from 100 mL/hr to 50 mL/hr). Otherwise dosing will be held until symptoms resolve and the subject should be premedicated for the next scheduled dose.
 
Subjects who develop Grade 2 toxicity despite adequate premedication should be permanently discontinued from further trial treatment administration.
	
Subject may be premedicated 1.5h (± 30 minutes) prior to infusion of pembrolizumab (MK-3475) with:
 
 Diphenhydramine 50 mg po (or equivalent dose of antihistamine). Acetaminophen 500-1000 mg po (or equivalent dose of antipyretic).
Grades 3 or 4 Grade 3: Prolonged (i.e., not rapidly responsive to symptomatic medication and/or brief interruption of infusion); recurrence of symptoms following initial improvement; hospitalization indicated for other clinical sequelae (e.g., renal impairment, pulmonary infiltrates) Grade 4: Life-threatening; pressor or ventilatory support indicated	
Stop Infusion. Additional appropriate medical therapy may include but is not limited to:
 
 IV fluids Antihistamines NSAIDS Acetaminophen Narcotics Oxygen Pressors Corticosteroids Epinephrine 
Increase monitoring of vital signs as medically indicated until the subject is deemed medically stable in the opinion of the investigator.
 
Hospitalization may be indicated.
 
Subject is permanently discontinued from further trial treatment administration.
	No subsequent dosing
Appropriate resuscitation equipment should be available in the room and a physician readily available during the period of drug administration.		

5.6.1.1 Supportive Care Guidelines for Events of Clinical Interest and Immune-related Adverse Events (irAEs)

Events of clinical interest of a potential immunologic etiology (irECIs) may be defined as an adverse event of unknown etiology, associated with drug exposure and consistent with an immune

Phase II Pembrolizumab Reirradiation

phenomenon. irAEs may be predicted based on the nature of Pembrolizumab, its mechanism of action, and reported experience with immunotherapies that have a similar mechanism of action. Special attention should be paid to AEs that may be suggestive of potential irAEs. An irAE can occur shortly after the first dose or several months after the last dose of treatment.

If an irAE is suspected, efforts should be made to rule out neoplastic, infectious, metabolic, toxin or other etiologic causes prior to labeling an adverse event as an irAE. Information on how to identify and evaluate irAEs has been developed. Subjects who develop a Grade 2 or higher irAE should be discussed immediately with the Sponsor.

Recommendations to managing irAEs not detailed elsewhere in the protocol are detailed in Table 4 and the irAE guidance document (attached Appendix).

Table 4: General Approach to Handling irAEs

irAE	Withhold/Discontinue Pembrolizumab?	Supportive Care
Grade 1	No action	Provide symptomatic treatment
Grade 2	May withhold Pembrolizumab	Consider systemic corticosteroids in addition to appropriate symptomatic treatment
Grade 3 and Grade 4	Withhold Pembrolizumab Discontinue if unable to reduce corticosteroid dose to < 10 mg per day prednisone equivalent within 12 weeks of toxicity	Systemic corticosteroids are indicated in addition to appropriate symptomatic treatment. May utilize 1 to 2 mg/kg prednisone or equivalent per day. Steroid taper should be considered once symptoms improve to Grade 1 or less and tapered over at least 4 weeks.

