3.2 Primary Study Endpoints

The primary endpoint is PFS, which measures the length of time from the first day of proton reirradiation +/- concurrent chemoradiation until progressive disease, death from any cause, or last patient contact.

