9.3.1 Analysis Endpoints

Primary

Progression Free Survival (PFS) per RECIST 1.1

Progression Free Survival is defined as the time from initiation of definitive therapy to the first documented disease progression per RECIST 1.1 based on radiologists' review or death due to any cause, whichever occurs first, or last patient follow-up that documented lack of disease progression. Patients who have not had disease progression or who have died, will be censored on the most recent clinical evaluation date that documented that they were progression-free.

Secondary

Overall Survival

Overall Survival (OS) is defined as the time from initiation of definitive therapy to death due to any cause or last patient contact alive. Subjects without documented death at the time of the final analysis will be censored at the date of the last follow-up.

Toxicity Determination

Tolerability of therapy will be determined on the basis of CTCAE adverse event reporting. Toxicity will be reported separately for definitive therapy and Pembrolizumab. For the definitive therapy phase, we will report on adverse events which are grade 3 or higher treatment-related toxicities or any grade of pneumonitis or esophagitis. For the Pembrolizumab phase, we will report all treatment-related toxicities.

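### Radiation allowed under 5.5.2 is a primary-outcome progression event there but is absent from the PFS definition in 9.3.1, so the two sections can give different PFS results

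*Combined protocol and SAP*

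**What the plan says.** Section 5.5.2 (Prohibited Concomitant Medications) lists radiation among the therapies barred "during the Pre-Pembrolizumab Screening and Pembrolizumab Treatment Phase of this trial". It then makes an exception: "Radiation therapy to a symptomatic solitary lesion or to the brain may be allowed after consultation with Sponsor", adding that this "would be regarded as a disease progression event for the primary outcome". It gives no event date. The same section closes by saying that subjects who "require the use of any of the aforementioned treatments for clinical management should be removed from the trial".

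Section 9.3.1 (Analysis Endpoints) defines the PFS event as "first documented disease progression per RECIST 1.1 based on radiologists' review or death due to any cause, whichever occurs first". Patients without such an event "will be censored on the most recent clinical evaluation date that documented that they were progression-free". Radiation is not mentioned.

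Section 3.2 measures PFS "until progressive disease, death from any cause, or last patient contact", also without mentioning radiation, and 9.4 (Statistical Methods) adds no rule for it.

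On follow-up, 3.1 stops disease assessment when non-study cancer treatment begins, while 4.4.2 says every patient is followed for PFS and OS.

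**The concern.** The 5.5.2 sentence is an endpoint rule placed in a medication section, and nothing in the statistical plan picks it up. An analyst working from 9.3.1 would not count such a patient as an event. Radiation given for symptoms need not coincide with RECIST progression on radiologists' review, so the two rules can classify the same patient differently.

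Section 9.3.1 also does not settle what happens instead. If disease follow-up continues (4.4.2), the radiation is ignored and later progression is counted. If follow-up stops at the new treatment (3.1), the patient is censored. The documents do not say whether radiation under the exception is non-study treatment for this purpose. That leaves three possible codings: event, ignored or censored. Censoring removes patients just as they develop symptoms, which is likely to be informative and lengthens estimated PFS. The trial is open-label, with one arm compared with a fixed historical median of 6 months, so no concurrent control absorbs the choice.

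**Working it through.** **1. One patient, three readings.** Take a patient irradiated to a symptomatic solitary lesion during pembrolizumab, with RECIST progression not yet documented.

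- 5.5.2: event (date unstated).
- 9.3.1 with 4.4.2: no event yet; counted at later RECIST progression or death.
- 9.3.1 with 3.1: censored at the last progression-free evaluation.

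**2. The plan's own power figure.** Section 9.4 gives n = 35, accrual A = 24 months, further follow-up F = 3 months, medians of 6 and 10 months, exponential survival, one-sided 5%, and 80% power.

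- Hazards: ln 2/6 = 0.1155 (null) and ln 2/10 = 0.0693 (alternative).
- P(event) = 1 - [exp(-λF) - exp(-λ(A+F))]/(λA), which is 0.761 (null) and 0.604 (alternative).
- Expected events: 35 × 0.761 = 26.6 and 35 × 0.604 = 21.1.
- Power on the log-hazard scale: Φ[(ln(10/6) - 1.645/√26.6) × √21.1] = Φ(0.88) = 81.1%. A cube-root transform gives 79.5%. A simulated one-sample log-rank test, z = (E - O)/√E with E = null hazard × total follow-up time, gives 78.0%.

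The stated 80% is reproduced. The point here does not dispute it.

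**3. Effect on the proof-of-principle test (n = 35).** The documents give no rate or timing for such radiation, so both are assumed. The true median is 10 months, and radiation falls uniformly between 20% and 100% of time to progression or death. Power is for the simulated log-rank test:

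| Share irradiated first | Ignored | Event (5.5.2) | Censored |
|---|---|---|---|
| 5% | 78% | 74% | 82% |
| 10% | 78% | 70% | 85% |

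At 10%, the gap between the event and censored codings is 85 - 70 = 15 points. If radiation instead comes at 80-100% of that time, coding it as an event lowers power by only about 1 point.

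The gain in power from censoring is not a real gain. With a true median of 6 months, the one-sided error is about 4% when radiation is ignored. Across the same two rates and both timing windows, censoring raises it to about 6-11%.

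**4. Effect on the primary analysis (n = 41).** Section 9.4 makes this a Kaplan-Meier estimate with a median and 95% CI, without a test. With a true median of 10 months and radiation uniform over the whole time to progression (again assumed), typical medians are:

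| Share irradiated first | Event | Ignored | Censored |
|---|---|---|---|
| 0% | 10.0 | 10.0 | 10.0 |
| 5% | 9.6 | 10.0 | 10.3 |
| 10% | 9.3 | 10.0 | 10.7 |

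Coding as event rather than ignored changed the estimated median in 38% of simulated trials at 5%, and in 60% at 10%.

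**The case against.** The best reply is that few patients can be affected. Section 3.1 calls for directed imaging when new symptoms arise between scans, so a symptomatic lesion would often be documented as RECIST progression at about the time of radiation. Section 4.2 excludes known brain metastases, so brain radiation would usually accompany a new lesion, which is progression anyway. The exception covers only two trial phases. The wording of 3.2 is not tied to RECIST and can be read together with 5.5.2, so the intended handling is stated and what is missing is a cross-reference and a date. All of this stands. It narrows the point to symptomatic lesions irradiated without documented RECIST progression, but it does not reconcile 5.5.2 with 9.3.1.

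Some stronger inferences are tempting and are not supported:

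- *That the primary results will differ.* They differ only if someone is irradiated before RECIST progression or death, and no rate is given.
- *That each affected patient moves the 41-patient test statistic by a full event.* That would be 1/√E, or 0.16-0.18 with E about 41 under the alternative and 31 under the null. About 79-87% of affected patients already have a later event, so mostly only their follow-up time shortens. With radiation at 20-100% of time to progression the average shift is about 0.08, and about 0.02 if radiation is late.
- *That the power of a 41-patient test falls from 84% to 80-76%.* Those figures follow from the 20-100% timing assumption, but 9.4 plans no test in 41 patients. The Study Summary attaches the power to 41; 9.4 attaches it to 35.
- *That the investigator alone decides on radiation.* Section 5.5.2 requires consultation with the sponsor.

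**Conclusion.** The inconsistency is real and concerns the primary endpoint: following 9.3.1 as written contradicts a rule that 5.5.2 states for that endpoint. Its practical size is unknown and may be nil. At assumed rates of 5-10%, treating radiation as an event rather than ignoring it costs the 35-patient test about 4-8 points of power (78% to 74-70%) if radiation can come early, and about 1 point if it comes late. The sharper risk is censoring, which favours the drug and raises the false-positive rate. For the 41-patient primary analysis, the effect is on the curve, median and interval only. The conclusion that the sections conflict needs none of these assumptions. The sizes rest on all of them, including exponential survival.

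**What to change.** Reconcile 3.2, 5.5.2 and 9.3.1. State in 9.3.1 that radiation given under the 5.5.2 exception is a PFS event, as 5.5.2 already provides. Date it at the start of radiation unless RECIST progression is documented earlier, and state that such patients are not censored for it. Refer to this rule from 3.2. Report PFS based on RECIST progression or death only as a sensitivity analysis, which needs disease assessment to continue after radiation, so 3.1, 4.4.2 and the removal sentence in 5.5.2 should be made consistent on follow-up. This concerns how the endpoint is counted, not whether or when radiation is given.

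The cost is a few lines of wording, a recorded radiation start date and one extra analysis. The PFS estimate may be slightly less favourable than under 9.3.1 as it stands.
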